4.1 Study Objectives

Primary Efficacy Objective:

Preliminary evaluation the efficacy of treatment with high-titer Anti- SARS-CoV-2 plasma versus control (standard plasma) in patients with COVID-19 respiratory symptoms.

Primary Safety Objective:

Evaluate the safety of treatment with high-titer anti-SARS-CoV-2 plasma versus control (standard plasma) in patients with COVID-19 respiratory symptoms.

Secondary Objectives:

Compare the anti-SARS-CoV-2 convalescent plasma and control (standard plasma) groups anti-SARS-CoV-2 titers at days 0, 1, 3, 7 and 14 (additional days 21 and 28 may be included, as available).

Compare the rates, levels and duration of SARS-CoV-2 RNA in NP swabs using RT-PCR amongst the anti-SARS-CoV-2 convalescent plasma and control (standard plasma) groups at days 0, 7 and 14. Other specimen types may be tested as available (*eg.*, BAL fluid, tracheal secretions, sputum, etc.) or when RT-PCR assays are validated for additional sources (*i.e.*, stool, blood).

4.2 Definitions

1. Enrolled: From time consented to participate until designated as a screen failure or have either been discontinued from the study or completed it.
2. Randomized: when a randomization number is assigned
3. Screen Failures: signed informed consent, but then determined to be ineligible or withdraws before being randomized
4. Discontinued: randomized, but then withdrawn by investigator or withdraws consent
5. Completed: Subjects are considered to have completed when they are followed through day 60 or have had an adverse event or death occurred prior to day 60.

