PROTOCOL SUMMARY:

Long title: Convalescent Plasma to Limit Coronavirus Associated Complications: A Randomized Open label, Phase 1 Study Comparing the Efficacy and Safety of High-Titer Anti-SARS-CoV-2 plasma vs. placebo in hospitalized patients with interstitial pneumonia due to COVID-19

Short title: CSSC-002

Clinical Phase: 1

IND Sponsor: Johns Hopkins via a national IND

Conducted by: Mayo Clinic in collaboration with Johns Hopkins University, Washington University in St. Louis and other interested parties.

Sample Size: 20

Study Population: Hospitalized COVID-19 patients aged 18 years of age with respiratory symptoms within 3 to 7 days from the beginning of illness.

Study Duration: April 1, 2020 to December 31, 2022

Study Design: This randomized placebo-controlled open label phase 1 trial will assess the efficacy and safety of anti-SARS-CoV-2 convalescent plasma in hospitalized patients with acute respiratory symptoms between 3 and 7 days after the onset of symptoms with or without confirmed interstitial COVID-19 pneumonia by chest CT. A total of 20 eligible subjects will be randomized in a 1:1 ratio to receive either high titer anti-SARS-CoV-2 plasma or control (standard thawed plasma)

The following will be assessed in all subjects:

- Age, sex, comorbidities, date of symptoms, source of infection, type of admission, APACHE score, SOFA score, Clinical status, vital signs including temperature, respiratory rate, oxygen saturation, oxygen requirement, CBC with neutrophil counts, lymphocytes count, CRP, chest x-ray, chest CT, location in hospital,
- Safety and efficacy: Day 0 (baseline), 1, 2, 3, 7, 14, and 28 and once monthly at 2-3 months.
- Serum or plasma antibody titer₁ to SARS-CoV-2: Day 0, 1, 3, 7, 14 (additional days 21 and 28 may be included, as available)

¹ Measured via initial anti-SARS-CoV-2 ELISA and serum neutralizing antibody titer to SARS-CoV-2.

- SARS-CoV-2 PCR from nasopharyngeal swabs: Day 0, 3, 7, 14 and at any time when there is clinical suspicion for COVID-19
- Outcome measures: increased O2 requirement (PaO2/FiO2 ratio or SpO2/Flo2), supplemental oxygen strategy (nasal cannula, , high flow nasal cannula, noninvasive ventilation, intubation and invasive mechanical ventilation, rescue ventilation i.e. neuromuscular blocking agents, prone positioning, corticosteroids, ECMO), vasopressors, renal support, ICU LOS, ICU mortality, Hospital LOS, Hospital mortality, 28 day mortality

Study Agent:

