5.3 Study population

Inclusion Criteria for Enrollment

1. Patients must be 18 years of age or older
2. Hospitalized with COVID-19 respiratory symptoms and confirmation via COVID-19 SARS-CoV-2 RT-PCR testing. Patient is willing and able to provide written informed consent and comply with all protocol requirements.
3. Patient agrees to storage of specimens for future testing.
4. If female must not be pregnant and/or breastfeeding.

Exclusion Criteria

1. Female subjects with positive pregnancy test, breastfeeding, or planning to become pregnant/breastfeed during the study period
2. Receipt of pooled immunoglobulin in past 30 days
3. Contraindication to transfusion or history of prior reactions to transfusion blood products

Table: Schedule of Events

Study period	Screen	Baseline	Transfusion	Follow-up				
Day	-1 to 0	0	0	1	3	7	14	28 ⁴
Eligibility								
Informed consent	x							
Demographic and Medical history	x							
COVID-19 symptom screen	x							
SARS-CoV-2 RT-PCR for eligibility	x							
Pregnancy test	x							
ABO ₃	x							
Study Drug Administration								
Randomization		x						
Drug infusion			X					
Study Procedures								
Vital signs	x	x	XXXX ⁴	x	x	x	x	
Physical examination	x		x	x		x		
Symptom screen	x	x	x	x	x	x	x	x
Concomitant medications	x	x	x					
Assessment with 7-point ordinal scale		x		x	x	x	x	x
Adverse event monitoring		x	x	x	x	x	x	x
Laboratory testing								
CBC and CMP		x		x		x	x	
SARS-CoV-2 RT-PCR ⁵		x			x	x	x	
SARS-CoV-2 antibody		x		x	x	x	x	
Blood for future testing		x		x	x	x	x	

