5. Important medical events that may not result in death, be life threatening, or require intervention or escalation of care may be considered a serious adverse event when, based upon appropriate medical judgment, they may jeopardize the subject and may require medical or surgical intervention to prevent one of the outcomes listed in this definition. Examples of such medical events include allergic bronchospasm requiring intensive treatment in an emergency room or at home, blood dyscrasias or convulsions that do not result in inpatient hospitalization.

Unexpected Adverse event: (UAE) An adverse reaction, the nature or severity of which is not consistent with the investigator's brochure.

Serious and Unexpected Suspected Adverse Reaction (SUSAR)

Unanticipated Problem (UP)

Unanticipated Problem that is not an Adverse Event (e.g. breaches of confidentiality, accidental destruction of study records, or unaccounted-for study drug.

Protocol Deviation: Deviation from the IRB-approved study procedures. Designated serious and non-serious

1. Serious Protocol Deviation: Protocol deviation that is also an SAE and/or compromises the safety, welfare or rights of subjects or others
2. Safety Reporting Requirements

Reporting Interval

All AEs and SAEs will be documented from the first administration of study product until completion or un-enrollment from the study. All AEs and SAEs will be followed until resolution even if this extends beyond the study-reporting period. Resolution of an adverse event is defined as the return to pre-treatment status or stabilization of the condition with the expectation that it will remain chronic.

At any time after completion of the study, if the investigator becomes aware of a SAE that is suspected to be related to study product

Investigator's Assessment of Adverse Events

The determination of seriousness, severity, and causality will be made by an on-site investigator who is qualified (licensed) to diagnose adverse event information, provide a medical evaluation of adverse events, and classify adverse events based upon medical judgment. This includes but is not limited to physicians, physician assistants, and nurse practitioners.

Laboratory abnormalities will be reported as AEs if there is a 2 s.d. increase above baseline.

Assessment of Seriousness

1. Event seriousness will be determined according to the protocol definition of an SAE
2. Assessment of Severity

Event severity will be assigned according to the scale below

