- 1 = Mild: Transient or mild discomfort (<48 hours); no medical intervention/therapy required.)
- 2 = Moderate: Some worsening of symptoms but no or minimal medical intervention/therapy required)
- 3 = Severe: Escalation of medical intervention/therapy required
- 4 = Life-threatening: Marked escalation of medical intervention/therapy required.
- 5= Death

Assessment of Association

The association assessment categories that will be used for this study are:

- Associated – The event is temporally related to the administration of the study product and no other etiology explains the event.
- Not Associated – The event is temporally independent of the study product and/or the event appears to be explained by another etiology.

The investigator must provide an assessment of association or relationship of AEs to the study product based on:

- Temporal relationship of the event to the administration of study product;
- Whether an alternative etiology has been identified;
- Biological plausibility;
- Existing therapy and/or concomitant medications.

13. Safety Oversight

Monitoring Plan

1. All AE and SAW will be reviewed by protocol team in real time.
2. A medical monitor will be appointed by the sponsor for safety oversight of the clinical study.
3. A data safety monitoring board (DSMB), led by **[name]** composed of independent experts without conflict of interests will be established. The Board will review the study before initiation and at least yearly thereafter. The Board will review study data to evaluate the safety, efficacy, study progress, and conduct of the study
4. An Independent Safety Monitor (ISM) will be appointed. The ISM is a physician with expertise in infectious diseases and whose primary responsibility is to provide timely independent safety monitoring. An ISM is in close proximity to the study site and has the authority to readily access study participant records. The ISM reviews any SAE that occurs at the study site in real time and provides a written assessment.

Study monitoring

1. As per ICH-GCP 5.18 and FDA 21 CFR 312.50, clinical protocols are required to be adequately monitored by the study sponsor. Monitors will verify that
 - a. There is documentation of the informed consent process and signed informed consent documents for each subject
 - b. There is compliance with recording requirements for data points
 - c. All SAEs are reported as required
 - d. Individual subjects' study records and source documents align

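### The definition of a completed subject, read with the AE reporting interval, ends capture of new AEs and SAEs at a subject's first AE, and contradicts the AE visits scheduled to day 90

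*Protocol*

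**What the plan says.** Section 4.2 (Definitions) counts subjects as "completed when they are followed through day 60 or have had an adverse event or death occurred prior to day 60". No seriousness, grade or causality is attached to the adverse event. The same section defines enrolled status as running "From time consented to participate until designated as a screen failure or have either been discontinued from the study or completed it", so enrolment also ends at completion.

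Section 12 (Reporting Interval): "All AEs and SAEs will be documented from the first administration of study product until completion or un-enrollment from the study". It adds: "All AEs and SAEs will be followed until resolution even if this extends beyond the study-reporting period". A further sentence, on SAEs found after the study, is limited to those suspected to be related that the investigator learns of, and it breaks off before stating an action.

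Other parts of the protocol plan a longer window. The schedule of events marks AE monitoring at baseline, transfusion and days 1, 3, 7, 14 and 28, and its footnote repeats the day 28 assessments on days 60 and 90. Section 9 lists AE evaluation on day 0, days 1 to 7, day 28, and days 60 and 90. The Protocol Summary has safety assessed monthly at 2 to 3 months.

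The schedule row "Concomitant medications" is marked only at screening, baseline and transfusion. Section 6.2 requires these medications on the CRF and gives no end date.

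**The concern.** An AE is defined broadly in Section 12: any untoward occurrence after the study intervention, related or not, and also a laboratory rise of 2 s.d. above baseline. Section 9 calls for daily CBC, metabolic panel and CRP over days 1 to 7. In hospitalized COVID-19 patients a first AE could come early and in many subjects, so a literal reader could close recording within days of transfusion.

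The primary safety endpoint in Section 8 is the cumulative incidence of SAEs over the study period, and Section 7.1.1 compares the proportions with an SAE and with a Grade 3 or higher AE by Fisher's exact test. If recording stops at a first AE, both depend on an event that occurs after treatment and may be affected by it. With 10 subjects per arm, one missed SAE patient moves an arm by 10 percentage points. Several halting criteria in Section 13 also depend on events being captured.

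**Working it through.** **Textual check.** The two windows, side by side:

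| Source | New AEs captured until |
|---|---|
| Sections 4.2 and 12 together, subject with an AE before day 60 | that AE |
| Sections 4.2 and 12 together, subject without one | day 60 (or death) |
| Schedule of events, its footnote, Section 9 | day 90, no exemption |

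Following known AEs to resolution does not capture new ones. Even for subjects with no AE, days 61 to 90 (30 of 90 days, one third) lie outside the Section 12 window but inside the visit schedule. The protocol gives no order of precedence.

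**Size if the literal rule were applied.** The protocol states no AE or SAE rate, so there is no figure to reproduce. The only input taken from it is 20 subjects at 1:1, so 10 per arm. Everything else is assumed:

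- e = probability of an early AE
- s = share of early AEs that themselves count as SAEs
- q = probability of a later SAE, independent of the early AE and equal in both arms

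Recorded SAE proportion = e·s + (1 − e)·q = q + e·(s − q).

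Proportion under full recording = q + e·s·(1 − q).

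Loss = full − recorded = e·q·(1 − s), which is never negative.

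With q = 0.30 and e = 0.80 versus 0.40, the recorded proportions are 0.80s + 0.06 versus 0.40s + 0.18. They are equal when 0.40s = 0.12, so s = 0.30. A milder contrast, e = 0.50 versus 0.10, is shown beside it (all entries are arm with more early AEs / other arm):

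| s | Recorded, 80% / 40% | Full, 80% / 40% | Recorded, 50% / 10% | Full, 50% / 10% |
|---|---|---|---|---|
| 0 | 6% / 18% | 30% / 30% | 15% / 27% | 30% / 30% |
| 0.1 | 14% / 22% | 35.6% / 32.8% | 20% / 28% | 33.5% / 30.7% |
| 0.3 | 30% / 30% | 46.8% / 38.4% | 30% / 30% | 40.5% / 32.1% |
| 0.5 | 46% / 38% | 58% / 44% | 40% / 32% | 47.5% / 33.5% |

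Because recorded = q + e·(s − q), the arm with more early AEs shows the lower rate only when s is below q. For s = 0 and e = 0.50 versus 0.10, varying q from 0.20 to 0.40 gives 10% versus 18% up to 20% versus 36%, where the truth is equal. In that setting with q = 0.30, exact binomial enumeration puts the chance that the arm with more early AEs shows fewer SAE patients at 65%, against 40% under full recording. If e is equal in the two arms, events are lost but neither arm is favoured.

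**The case against.** The strongest reply is that sites work from the visit schedule, which asks for AE evaluation at every visit and excuses nobody. The independent safety monitor in Section 13 reviews any SAE at the site in real time, whatever the subject's completion status. Section 8 lists 60-day mortality, which follow-up ending at a first AE could not supply. This stands as far as it goes: a reader might infer that later SAEs will certainly go unrecorded, and the documents do not support that. They contain two incompatible windows, and later events may well be captured in practice. The reply does not remove the contradiction, because sites could apply different windows.

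A reader might also infer that the arm with more early reactions will look safer. That is not established either. Section 6.1 calls most plasma reactions relatively minor, which suggests a low s, but Section 8 lists fever and rash within the SAE endpoint, which would raise s and could turn the recorded comparison against that arm. Both arms receive plasma (Section 5.5), and many early AEs may come from the disease, so a twofold difference in early AEs has no support in the protocol.

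On medications, a reader might infer from the schedule that co-treatment after day 0 cannot be seen. Section 6.2 has no day 0 cutoff, Section 16 requires the medical records to show medications given, and corticosteroids appear among the outcome measures ("neuromuscular blocking agents, prone positioning, corticosteroids, ECMO"). What remains is a schedule row narrower than Section 6.2, although the causality assessment in Section 12 relies on "Existing therapy and/or concomitant medications".

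**Conclusion.** The definition is wrong as written and conflicts with the protocol's own visit schedule. Taken literally, Sections 4.2 and 12 end capture of new events at the first AE, or at day 60 at the latest, and undercount later SAEs in the primary safety endpoint and both Fisher comparisons. Whether events are actually lost depends on which text sites follow, which the protocol leaves open.

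The size can only be illustrated. The loss in an arm is e·q·(1 − s), and the protocol gives none of these quantities, overall or by arm, so neither the amount nor the direction of a between-arm bias is fixed. With equal later risk and equal s, the arm with more early AEs loses more events, yet it shows the lower recorded rate only if s is below q (break-even 30% when q is assumed to be 30%). The 6% versus 18% result is the extreme case in which no early AE counts as an SAE; it is not an estimate for this trial. The concomitant-medication row is a minor alignment point.

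**What to change.** 1. In Section 4.2, delete the adverse-event clause from the definition of completed and keep death.
2. In Section 12, state that all AEs and SAEs are recorded for every subject, regardless of earlier AEs, through one fixed end date that matches the scheduled visits. Day 90 is the natural candidate, because it is the last visit at which AE evaluation is already scheduled. The protocol does not itself settle day 60 against day 90, so the sponsor must choose and say so.
3. Align the day 60 in the completion definition with that date.
4. Minor: bring the concomitant-medication row of the schedule into line with Section 6.2.

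The cost is wording in two sections and one table row, plus slightly more AE recording at visits already planned.

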5.3 Study population

Inclusion Criteria for Enrollment

1. Patients must be 18 years of age or older
2. Hospitalized with COVID-19 respiratory symptoms and confirmation via COVID-19 SARS-CoV-2 RT-PCR testing. Patient is willing and able to provide written informed consent and comply with all protocol requirements.
3. Patient agrees to storage of specimens for future testing.
4. If female must not be pregnant and/or breastfeeding.

Exclusion Criteria

1. Female subjects with positive pregnancy test, breastfeeding, or planning to become pregnant/breastfeed during the study period
2. Receipt of pooled immunoglobulin in past 30 days
3. Contraindication to transfusion or history of prior reactions to transfusion blood products

Table: Schedule of Events

Study period	Screen	Baseline	Transfusion	Follow-up				
Day	-1 to 0	0	0	1	3	7	14	28 ⁴
Eligibility								
Informed consent	x							
Demographic and Medical history	x							
COVID-19 symptom screen	x							
SARS-CoV-2 RT-PCR for eligibility	x							
Pregnancy test	x							
ABO ₃	x							
Study Drug Administration								
Randomization		x						
Drug infusion			X					
Study Procedures								
Vital signs	x	x	XXXX ⁴	x	x	x	x	
Physical examination	x		x	x		x		
Symptom screen	x	x	x	x	x	x	x	x
Concomitant medications	x	x	x					
Assessment with 7-point ordinal scale		x		x	x	x	x	x
Adverse event monitoring		x	x	x	x	x	x	x
Laboratory testing								
CBC and CMP		x		x		x	x	
SARS-CoV-2 RT-PCR ⁵		x			x	x	x	
SARS-CoV-2 antibody		x		x	x	x	x	
Blood for future testing		x		x	x	x	x	

5.4 Subject Withdrawal

1. Subjects can terminate study participation and/or withdraw consent at any time without prejudice.
2. Randomized subjects who withdraw from the study will not be replaced.
3. The investigator may withdraw subjects if they are lost to follow up, non-compliant with study procedures or if the investigator determines that continued participation in the study would be harmful to the subject or the integrity of the study data
4. Discontinuation of the study: The study sponsor, FDA and IRB all have the right to terminate this study at any time

³ At least 2 assessments of ABO type on file, with one in the 90 days prior to enrollment

⁴ Vital sign testing: Immediately prior to infusion, 10-20 minutes after start of infusion, at completion of infusion and 30-60 minutes after the end of the infusion

⁵ Sites could include nasopharyngeal and throat

⁴The assessments performed on day 28 will be repeated on days 60 and 90.

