Samples would not be shared with investigators other than investigators at Mayo unless outside investigators had relevant assays or expertise not available to the study investigators. The specimens would remain linked and at Mayo for 5 years. Any use of these specimens not specified in the current protocol will be reviewed by the Mayo IRB.

16. Data management and monitoring

a. Source Documents

The primary source documents for this study will be the subjects' medical records. If the investigators maintain separate research records, both the medical record and the research records will be considered the source documents for the purposes of auditing the study. The investigator will retain a copy of source documents. The investigator will permit monitoring and auditing of these data, and will allow the sponsor, IRB and regulatory authorities access to the original source documents. The investigator is responsible for ensuring that the data collected are complete, accurate, and recorded in a timely manner. Source documentation (the point of initial recording of information) should support the data collected and entered in to the study database and must be signed and dated by the person recording and/or reviewing the data. All data submitted should be reviewed by the site investigator and signed as required with written or electronic signature, as appropriate. Data entered into the study database will be collected directly from subjects during study visits or will be abstracted from subjects' medical records. The subjects' medical records must record their participation in the clinical trial and what medications (with doses and frequency) or other medical interventions or treatments were administered, as well as any AEs experienced during the trial.

Data Management Plan

Study data will be collected at the study site(s) and entered into the study database. Data entry is to be completed on an ongoing basis during the study.

b. Data Capture Methods

Clinical data will be entered into a database which includes password protection and internal quality checks to identify data that appear inconsistent, incomplete, or inaccurate.

c. Study Record Retention

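### Withdrawal by the investigator for non-compliance closes recording of new adverse events after a single Day 0 infusion, and no rule keeps outcome follow-up going

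*Protocol*

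**What the plan says.** Four parts of the protocol act together.

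- **Grounds for withdrawal (section 5.4).** "The investigator may withdraw subjects if they are lost to follow up, non-compliant with study procedures". A further ground is the investigator's judgement that "continued participation in the study would be harmful to the subject or the integrity of the study data". Neither non-compliance nor data integrity is given criteria. The same section adds: "Randomized subjects who withdraw from the study will not be replaced".
- **Status after withdrawal (section 4.2).** "Discontinued: randomized, but then withdrawn by investigator or withdraws consent". A subject counts as enrolled only until they "have either been discontinued from the study or completed it".
- **Safety reporting window (section 12, Reporting Interval).** "All AEs and SAEs will be documented from the first administration of study product until completion or un-enrollment from the study". The next sentence limits the effect: "All AEs and SAEs will be followed until resolution even if this extends beyond the study-reporting period".
- **Source of data (section 16, Source Documents).** "The primary source documents for this study will be the subjects' medical records".

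The setting matters too. The Protocol Summary describes an open-label trial of 20 patients randomised 1:1. The Schedule of Events and section 9 show one plasma administration, on Day 0. Assessments, including adverse events, continue to days 60 and 90. Section 8 makes the cumulative incidence of SAEs over the study period a primary safety endpoint and lists 60-day mortality among the secondary endpoints.

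**The concern.** In a trial with continuing treatment, non-compliance can be a reason to stop the treatment. Here the treatment is over on Day 0. What remains is observation, and a missed swab or visit is no reason to stop recording ICU admission, death or SAEs in someone already exposed to the product. The protocol does not separate stopping study procedures from ending follow-up, so one act by the investigator does both.

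The person with this discretion can know the arm. If withdrawals differ between arms, or follow from how patients are doing, later events are lost unequally and the comparison of randomised groups is biased.

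There is also a direct safety consequence. Section 13 halts enrolment and dosing for review if one subject has an SAE associated with the study product. If such an SAE arises after withdrawal and is not documented, that criterion may not be triggered.

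**Working it through.** **Step 1. Does withdrawal close the window?** Section 5.4 permits withdrawal for non-compliance. Section 4.2 classes a randomised subject withdrawn by the investigator as discontinued, and enrolment lasts only until discontinuation or completion. Section 12 documents AEs and SAEs until completion or un-enrolment. Un-enrolment has no definition of its own, so I read it as the end of enrolment in section 4.2. On that reading the window for new events closes at withdrawal. I found no text that reopens it or keeps outcomes under collection for a patient who still consents.

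**Step 2. Inputs for size.** The protocol gives no alpha, power, event rate or dropout allowance, so it has no power figure to reproduce. The one check available is 20 / 2 = 10 per arm, which agrees with n = 10 per cohort in section 7.1.

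- From the protocol: 10 per arm; Fisher's exact test for the proportion with an SAE (section 7.1.1); Clopper-Pearson intervals (section 7.1).
- Assumed by me: the event counts, a two-sided test, a 0.05 level and 95% intervals.

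**Step 3. Weight of one patient.** 1/10 = 10 percentage points of an arm.

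**Step 4. Fisher's test.** Suppose that full follow-up would show SAEs in 1/10 active and 5/10 control patients (6 events in 20).

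- P(1 in active) = C(10,1) × C(10,5) / C(20,6) = 10 × 252 / 38,760 = 0.0650
- P(0 in active) = C(10,6) / C(20,6) = 210 / 38,760 = 0.0054
- One tail = 0.0704; the arms are equal, so two-sided p = 2 × 0.0704 = **0.141**

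Now let the one active event occur after withdrawal and go unrecorded, with the patient kept in the denominator: 0/10 vs 5/10 (5 events in 20).

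- P(0 in active) = C(10,5) / C(20,5) = 252 / 15,504 = 0.01625
- Two-sided p = 2 × 0.01625 = **0.033**

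If the patient were dropped instead, giving 0/9 vs 5/10, p = (252 + 126) / C(19,5) = 378 / 11,628 = 0.033. The choice of denominator does not alter the result here.

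**Step 5. Direction.** The error can run either way. If one control event is missed instead, 1/10 vs 4/10 gives p = 2 × (10 × 210 + 252) / 15,504 = 0.30.

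**Step 6. Interval for one arm.** For 1/10 the 95% Clopper-Pearson interval is 0.3% to 44.5%. For 0/10 the upper limit is 1 − 0.025^(1/10) = 30.8%. Missing a single event lowers the upper bound on the event rate from 44.5% to 30.8%.

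**The case against.** The case against has force on several points, each of which limits what may be concluded.

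- **Events already observed are not deleted.** A reader might infer that an investigator could remove patients who have already gone to the ICU, turning 3/10 vs 3/10 into 1/8 vs 3/10 (12.5% vs 30%). The protocol does not support this. Nothing in it discards data collected before withdrawal, the medical record is the primary source, and section 7.1 fixes 10 as the denominator. Only events after withdrawal are at risk.
- **Adverse event follow-up does not stop altogether.** Events already recorded are followed to resolution. Section 12 also begins a sentence on related SAEs learned of after study completion, but it breaks off in the text available and speaks of completion, not withdrawal.
- **Loss of efficacy outcomes is inferred.** No section says that ICU admission or vital status ceases to be collected. The inference rests on the definitions and on the absence of a rule to continue.
- **Non-replacement is not a defect.** It fits an analysis of all 20 randomised patients.
- **The practical scope is limited.** The clause is permissive. Patients are in hospital when most ICU admissions would arise. Section 13 provides a medical monitor, a DSMB and an independent safety monitor with access to participant records. Efficacy evaluation is described as preliminary, and AE analysis as primarily descriptive.

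These points narrow the concern but do not remove it. The reporting window is a data collection rule in the protocol. A statistical analysis plan can define who is analysed, but it cannot recover events that were never recorded. Oversight bodies see what is documented, and section 12 does not require documentation after un-enrolment.

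**Conclusion.** The concern holds in a limited form. As written, the protocol lets an investigator who can know the arm withdraw an exposed patient for non-compliance. New AEs and SAEs then need not be documented, and nothing requires other outcomes to be followed. With 10 fixed as the denominator, that patient may appear as event-free.

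The size is 10 percentage points of an arm per affected patient. In the illustration, one missed event moves p from 0.14 to 0.03, or from 0.14 to 0.30 if the missed event is in the control arm. These figures rest on assumed counts and an assumed two-sided 0.05 level. They show how sensitive the trial is, not what to expect. The verdict also rests on reading un-enrolment as the end of enrolment in section 4.2.

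A reader might go further and conclude that the randomised comparison is already broken, or that withdrawal would be used to favour one arm. The document shows no misuse; the defect is that the rule allows events to be lost. It should be corrected because the trial is small, safety is a primary objective and the change is cheap.

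**What to change.** 1. **Section 5.4.** Limit non-compliance with study procedures to a reason for stopping further study samples or visits, not for ending participation in follow-up.
2. **Section 12, Reporting Interval.** State that, unless the patient withdraws consent for follow-up or record access, AEs and SAEs, ICU admission, respiratory support and vital status are collected through Day 90 for every randomised patient. The sources are the medical record and, where the patient agrees, a phone call.
3. **Section 4.2.** Align the definitions of enrolled and discontinued with items 1 and 2. Completion is defined there as follow-up to day 60, or an earlier adverse event or death. Since section 12 also closes the window at completion, that definition needs reconciling with the Day 90 assessments at the same time.

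The cost is a few sentences of protocol text and some record abstraction for at most a few patients. The change will not recover everything. Section 9 plans the Day 28 contact by phone, and outcomes after discharge may not reach the hospital record, so some will still be missing for patients who stop cooperating.
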